2. Age 50 or over
3. Increased optic nerve cupping regardless of IOP in one or both eyes
4. Corrected visual acuity 20/40 or better in both eyes
5. Early to moderate perimetric changes defined as a mean deviation (MD) no less than -7.5 and a pattern standard deviation (PSD) no greater than +7.5 in the worse eye.

Subjects with moderate to advanced glaucoma

1. Male of Female
2. Age 50 or older
3. Increased optic nerve cupping regardless of IOP in one or both eyes
4. Grossly abnormal automated perimetry (MD less than -7.5 or PSD greater than +7.5 in the worse eye)
5. Best-corrected visual acuity of 20/40 or better in both eyes

Exclusion Criteria:

Normal Controls:

1. glaucoma or glaucoma suspicion in either eye
2. IOP > 21 in either eye
3. History of use of IOP-reducing drops in either eye except temporarily following cataract extraction
4. History of any ocular surgery except cataract extraction or refractive surgery (LASIK, ORK, or equivalent) in either eye
5. Retinal disease in either eye
6. Abnormal measured automated perimetry in either eye

7. Abnormal measured contrast sensitivity in either eye

F2. Procedure

The protocol is divided into two studies that will have two separate consent forms (Study 1A and B, and Study 2).

All participants requiring spectacle correction will use their own glasses or contact lenses or a pair of provided trial glasses (if needed) during the research study.

Study 1: Subjects participating in this portion of the study will attend one single visit:

1) Informed consent will be obtained and inclusion/exclusion criteria will be confirmed. Demographic information, ocular history, refraction, and visual acuity information will be collected for all patients. Additional clinical data will also be collected for Study 1B participants only. Information to be collected will include name, date of birth, ethnicity, gender, ocular history (surgery, etc), type of glaucoma (study 1B), current visual acuity, refraction, central corneal thickness (study 1B), intraocular pressure (study 1B), recent slit lamp exam including lens status (study 1B), recent dilated exam including optic nerve appearance (study 1B), and recent automated perimetry results (Humphrey visual field, study 1B)

2) Snellen visual acuity will be measured while wearing current spectacle correction to ensure acuity of 20/40 or better. The current spectacle correction (refraction) and acuity will be recorded.

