3) OKR-based contrast testing will be performed with the OCD - optokinetic contrast device (the device in study with this protocol). Subjects will be shown a brief demonstration of the OCD under infrared light (to begin dark adaptation) to familiarize themselves with the device and the expected testing strategy.

4) Subjects will then be dark adapted for 20-30 minutes. During this time they will be sitting in a darkened room. If the room is not dark enough a loose blindfold may be used. Music options will be available to help pass the time and ease potential discomfort.

5) After 20-30 minutes, the blindfold will be removed (if used) and patient will have monocular dark-adapted (scotopic) testing done with the OCD, left eye followed by right eye. The non-tested eye may be covered during testing. After scotopic testing, the light of the OCD will be increased and light-adapted (photopic) testing will be performed in the same manner.

6) Debriefing. Subjective assessments of the testing modality and dark adaptation process will be collected.

This visit should take approximately 60 minutes to complete.

Study 2:

Study subjects participating in this portion of the study will require two study visits.

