1) Humphrey standard automated perimetry (visual field testing). This is a form of static perimetry used to assess retinal function and sensitivity. It is a commonly used photopic testing modality for the diagnosis and status of glaucoma and used frequently throughout ophthalmology and many ophthalmologic clinical studies. We hypothesize that there will be similarities in performance between Humphrey automated perimetry and OKR testing which will help validate our testing strategy. For patients with glaucoma, for whom visual field testing is frequently performed, this test will not be performed if a high-quality visual field test has been obtained within the last 6 months. For such patients, the visual field test from the

clinical record will be used in the study.

2) OKR-based contrast testing will be performed with the OCD - optokinetic contrast device (the device in study with this protocol). Subjects will be shown a brief demonstration of the OCD under infrared light (to begin dark adaptation) to familiarize themselves with the device and the expected testing strategy.

3) Subjects will then be dark adapted for 20-30 minutes. During this time they may be blindfolded (depending on darkness of the room) and sitting in a dark room. Music options will be available to help pass the time and ease potential discomfort.

4) After 20-30 minutes, the blindfold will be removed (if used) and patient will have monocular dark-adapted (scotopic) testing done with the OCD, left eye followed by right eye. The non-tested eye may be covered during testing.

5) After scotopic testing, the light of the OCD will be increased and light-adapted (photopic) testing will be performed in the same manner.

This visit should take approximately 90 minutes to complete.

Second Research Visit (approximately 1 month after the first research visit):

1) Pelli-Robson Contrast Sensitivity Testing. This is a form of stationary central vision contrast sensitivity that is a commonly used testing modality for photopic contrast in many ophthalmologic clinical studies. We hypothesize that there will be similarities in contrast performance between Pelli-Robson and OKR testing which will help validate our testing strategy.

2) OKR-based contrast testing. This will be performed as in the second visit described above except that the testing order will be the right eye first, followed by the left eye.

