20 normal patients and 20 participants with definite glaucoma should provide enough of a baseline for the 4 disease groups as the number of participants in each of the disease groups is of relatively large size.

Study 2: 20 participants will be enrolled in each of the five groups described in the Section F2 Procedures section (N=100). If the study team is able to establish intrasubject reliability of testing, the number of subjects needed in Study 2 may be decreased with a future amendment submission.

G2. Data Analysis

Provide a description of your plan for data analysis. State the types of comparisons you plan (e.g. comparison of means, comparison of proportions, regressions, analysis of variance). Which is the PRIMARY comparison/analysis? How will the analyses proposed relate to the primary purposes of your study?

Study 1 and 2: Statistical comparison of the study groups will be performed using a combination of pairwise and multivariate analyses. A sample size estimate is not possible at this time as the ranges of contrast sensitivity are not yet determined due to uncertainty of the testing parameters. The normative database will be critical for the design of larger scale future studies.

The primary expected comparisons are as follows:

Intra-patient:

- 1) Comparison of scotopic contrast between the two eyes
- 2) Comparison of photopic contrast between the two eyes
- 3) Comparison of scotopic to photopic contrast within each eye
- 4) Comparison of intraocular scotopic to photopic contrast ratio (3 above) between the two eyes
- 5) Comparison of 1-4 to automated perimetry testing (Study 2 only)
- 6) Comparison of 1-4 to Pelli-Robson testing (Study 2 only)

Interpatient:

Comparison of 1-6 above among all patients and groups.

For subjects in Study 2, longitudinal data will be collected for 5 years after participation to track clinical progression of glaucoma where present.

Interim analysis will be performed after the first 5 patients of Study 1A have been enrolled to ensure that the device hardware and software are properly functioning.

Interim analysis will be performed after the first 10 patients for both Study 1A and Study 1B have been enrolled to ensure that the device hardware and software are properly functioning .

Interim analysis will be performed after the completion of Study 1 to determine if the study sample size of Study 2 is appropriate.

Section H: Potential Risks/Discomforts

H1. Potential Risks/Discomforts

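### In Study 1 every participant is tested left eye first at a single visit, so the mean left-right difference cannot be separated from test order

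*Combined protocol and SAP*

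**What the plan says.** F2 Procedure, Study 1, states: "Subjects participating in this portion of the study will attend one single visit". At that visit, step 5 specifies "monocular dark-adapted (scotopic) testing done with the OCD, left eye followed by right eye", after which "light-adapted (photopic) testing will be performed in the same manner". On occlusion, the same step says only: "The non-tested eye may be covered during testing". No randomised, alternating or reversed eye order is given for Study 1. G1 allows a Study 1 participant to be retested only for technical problems and mentions no change of order.

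G2 Data Analysis covers Studies 1 and 2 together. Its primary expected comparisons include:

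- item 1: "Comparison of scotopic contrast between the two eyes"
- item 2: "Comparison of photopic contrast between the two eyes"
- item 4: "Comparison of intraocular scotopic to photopic contrast ratio (3 above) between the two eyes"

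Only items 5 and 6 (perimetry and Pelli-Robson) are restricted to Study 2, so items 1, 2 and 4 apply to Study 1.

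In Study 2 the second research visit repeats the testing "except that the testing order will be the right eye first, followed by the left eye".

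**The concern.** If Study 1 shows that right eyes score differently from left eyes on average, the investigators cannot tell whether this comes from the eyes or from the sequence. The protocol's own procedure suggests ways a second test could differ from a first: practice, fatigue and, in scotopic testing only, a few more minutes in the dark. The last depends on whether the untested eye is covered, which is optional and so may vary between participants.

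Timing matters too. F1 Design presents Study 1 as the stage at which problems are found and adjustments made before Study 2 begins. A sequence effect is the kind of problem Study 1 should expose, but as written it cannot be distinguished from an eye effect.

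**Working it through.** **Inputs.** 20 participants in 1A and 20 in 1B (F1); one visit, left then right in both light conditions (F2); 3-5 minutes per eye (Section C); 20-30 minutes of dark adaptation (F2, step 4). The plan states no alpha, SD or effect size, so it has no figure of its own to reproduce.

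**What the mean difference estimates.** Let *D* be right minus left for one participant, *e* the eye effect and *o* the effect of being tested second.

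- Study 1 as written: everyone has E(*D*) = *e* + *o*. There is one equation for two unknowns, whatever the sample size.
- First eye split 10/10: left-first participants have E(*D*) = *e* + *o*, and right-first participants have E(*D*) = *e* − *o*. The average of the two group means gives *e*; half their difference gives *o*.
- Study 2: visit 1 gives *e* + *o*, and visit 2 gives *e* − *o*. The two separate if each effect is the same at both visits.

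**Rank check.** The columns are one per participant, plus eye, plus second test (and visit in Study 2).

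| Design | Columns | Rank |
|---|---|---|
| Study 1 fixed order, n = 20 | 22 | 21 |
| Study 1 fixed order, n = 40 | 42 | 41 |
| Study 1 alternated, n = 20 | 22 | 22 |
| Study 1 alternated, n = 40 | 42 | 42 |
| Study 2 as written, n = 100 | 103 | 103 |

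**What is and is not affected.**

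- Items 1 and 2: the mean signed difference is *e* + *o*.
- Item 4: on a log scale the order effect in the ratio is *o*(scotopic) − *o*(photopic). It vanishes only if the order effect is proportionally equal in both light conditions.
- 1A versus 1B: the contrast of mean differences contains *o*(1A) − *o*(1B), which is zero if the order effect is the same in both groups.
- The spread of the interocular differences is unchanged by a constant *o*.

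**Extra dark time, scotopic only.** 3/30 = 10% to 5/20 = 25% more time for the second eye. This is time, not sensitivity, and it is approximate. Adaptation already begins during the infrared demonstration, and Section C does not say whether 3-5 minutes covers one light condition or both; either point could lower the figure.

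**Illustrative error rate.** Assume no true eye difference, a two-sided 5% paired *t* test with n = 20 (19 df), an order effect δ in SDs of one eye's score, and between-eye correlation ρ. The standardised difference is d = δ/√(2(1−ρ)), with noncentrality d√20. For example, δ = 0.2 and ρ = 0.8 give d = 0.2/√0.4 = 0.316 and noncentrality 1.41, hence 26.9% rejections. Both δ and ρ are assumptions.

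| δ | ρ = 0.5 | ρ = 0.6 | ρ = 0.7 | ρ = 0.8 |
|---|---|---|---|---|
| 0.1 | 7.1% | 7.6% | 8.5% | 10.3% |
| 0.2 | 13.6% | 15.8% | 19.5% | 26.9% |
| 0.3 | 24.7% | 29.7% | 37.6% | 52.1% |

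Pooling all 40 makes this worse. At ρ = 0.5, the rates for δ = 0.2 and 0.3 rise to 23% and 46%.

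**After the fix.** With a 10/10 split and order in the model, simulation (100,000 runs at each of δ = 0.1 and 0.3, ρ = 0.5 and 0.8) gave 5.0%-5.1% rejections. The variance of the eye estimate is σ²(1/10 + 1/10)/4 = σ²/20, where σ² is the variance of *D*; this is the same as with fixed order. Only the degrees of freedom fall from 19 to 18, so the confidence interval widens by 2.1009/2.0930 = 1.004, or 0.4%.

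**The case against.** The best reply is that the plan never names a mean signed left-right difference, a paired *t* test or a 5% level. The stated hypotheses concern reduced contrast sensitivity in glaucoma and similarity to perimetry and Pelli-Robson, not a population difference between left and right eyes. If the between-eye items mean individual asymmetry, better versus worse eye, or group contrasts, a constant order effect does little or no harm. In healthy 1A volunteers, a systematic difference would most naturally be blamed on sequence. A fixed order is also reasonable standardisation for a pilot, and a sentence declining to read the Study 1 mean difference as an eye effect would deal with the matter.

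Much of this stands as a limit on the consequences. It does not remove the problem. The items are listed as primary for Study 1 without a definition that avoids the mean difference. Blaming sequence in 1A would be an assumption that the design cannot test.

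Alternation also has a cost: it adds δ² to the variance of raw interocular differences. At δ = 0.3 and ρ = 0.8 the variance goes from 0.40 to 0.49, so the SD is √(0.49/0.40) = 1.107 times as large, about 11% more. The order term in the model removes this, but unadjusted ranges would show it.

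**Conclusion.** The concern holds. In Study 1, eye and test order are completely aliased for the mean signed left-right difference, and this follows from the procedure alone, without assumptions. The size of any resulting error is unknown because the documents give no order effect; the 7% to 52% rejection rates across δ = 0.1 to 0.3 are illustrations.

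The scope is narrow. The spread of interocular differences is unaffected by a constant order effect, and the 1A versus 1B contrast is biased only if that effect differs between groups. Study 2 can separate the two, provided the eye and order effects are each the same at both visits. Study 1 is not invalidated as an optimisation pilot. The change is worth making because it is cheap and matches the order reversal already used in Study 2.

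**What to change.** **Study 1.** Randomise or alternate which eye is tested first, balanced 10/10 within 1A and 10/10 within 1B. Keep the same first eye for scotopic and photopic testing in a given participant. Record the order and include it in every between-eye analysis; report interocular spread after adjustment for order. This needs a printed list, one recorded variable and one degree of freedom per sub-study, with no extra testing time, staff or participants.

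**Study 2.** No design change. Add a sentence to G2 saying that the between-eye and test-retest models use both visits and include test order and visit, and that the order effect is assumed equal at both visits.

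If the fixed order is kept in Study 1, G2 should at least say that its mean left-right difference will not be interpreted as an eye effect. That avoids a wrong conclusion but leaves any sequence effect unmeasured before Study 2.

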Describe and assess any potential risks/discomforts; (physical, psychological, social, legal, or other) and assess the likelihood and seriousness of such risks:

Only minimal risk is present as there is a small chance of loss of confidentiality as with any study. Study personnel attempt to minimize this risk.

The only contact the participant has with the device is via the chin rest and forehead rest, which are standard equipment purchased from an ophthalmic device supplier. There is no other contact with the device required.

There is no risk associated with the small infrared (IR) light used in this protocol, A dim LED-generated infrared (IR) light source is used during examination. The amount of light, power and thermal levels emitted from the device used in this study is less than international standards (IEC 60825-1) set for this type of light (IR exempt).

The use of a blindfold during dark-adaptation is potentially uncomfortable. This will be positioned very gently and the ambient light dark as well with music of the participant's choice playing to minimize discomfort. It may be possible to use a patch instead of a blindfold for participants who are particularly uncomfortable, but this will slow the process down slightly.

H2. Data and safety monitoring plan

Do the study activities impart greater than minimal risk to subjects?

No

H3. Coordination of information among sites for multi-site research

Is the BCM Principal Investigator acting as the SPONSOR-INVESTIGATOR for this multi-site research?

No or Not Applicable

Is BCM the COORDINATING CENTER for this multi-site research?
No or Not Applicable

Section I: Potential Benefits

Describe potential benefit(s) to be gained by the individual subject as a result of participating in the planned work.
There is no direct benefit to subjects for their participation in the study.

Describe potential benefit(s) to society of the planned work.

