This device qualifies as a non-significant device for several reasons in accordance with 812.2: A) It is not a significant risk device. Study participants will only have contact with a chin and forehead rest and eye movements recorded with a camera in response to a stimulus on a screen about 1 meter away. The device consists of the following: A computer monitor (old CRT), a camera to observe the eye, an infrared (IR) lighting source, a chin rest (from an old ophthalmic slit lamp), a screen to block one of the eyes, and an adjustable table (from an ophthalmic retailer). This IR source is a series of readily available low intensity IR LEDs that are mounted together and powered in unison. A commercially available ground glass diffuser sits in front of the LEDs to spread the light. There is no opportunity for pain, discomfort, or damage to the eyes in any way. The device is investigational and will not be used to make a clinical diagnosis. It is one of a kind and not currently meant for distribution. There is no more than minimal risk to subject. B) The device will be labeling in accordance with 812.5, stating: "CAUTION--Investigational device. Limited by Federal (or United States) law to investigational use." C) Informed consent will state clearly that this is an investigational device only. D) Investigators will comply with the requirements of 812.46 with respect to monitoring investigations and notify the IRB immediately of any unexpected finding or realization that the device may represent more than minimal risk. E) The study coordinator will maintains the records required under 812.140(b) (4) and (5) - The name and intended use of the device and the objectives of the investigation; - A brief explanation of why the device is not a significant risk device: - The name and address of each investigator: - The name and address of each IRB

that has reviewed the investigation: - A statement of the extent to which the good manufacturing practice regulation in part 820 will be followed in manufacturing the device; and - Any other information required by FDA. - Records concerning adverse device effects (whether anticipated or unanticipated) and complaints and will make the reports required under 812.150(b) (1) through (3) and (5) through (10); F) The study coordinator and investigators will ensure that participating investigators maintain the records required by 812.140(a)(3)(i) and make the reports required under 812.150(a) (1), (2), (5), and (7);

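### Adaptation state is not standardised in either study, and in Study 1 eye is confounded with time in the dark; the direction is clear but the size is unknown

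*Combined protocol and SAP*

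**What the plan says.** Section F2 uses almost the same wording for Study 1 (steps 4-5) and Study 2, Research Visit 1 (steps 3-5).

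- **Dark adaptation.** "Subjects will then be dark adapted for 20-30 minutes". No rule says when within that window testing starts. Room darkness is not defined. For Study 1, "If the room is not dark enough a loose blindfold may be used"; for Study 2, "During this time they may be blindfolded (depending on darkness of the room) and sitting in a dark room". Section H1 adds: "It may be possible to use a patch instead of a blindfold for participants who are particularly uncomfortable". It says that this slows the process slightly but gives no adjusted time.
- **Eye order.** In Study 1 and at Study 2 Visit 1, the "patient will have monocular dark-adapted (scotopic) testing done with the OCD, left eye followed by right eye". At the second Study 2 visit the right eye goes first.
- **Covering.** "The non-tested eye may be covered during testing". The device description in Section P lists "a screen to block one of the eyes", but F2 does not require its use.
- **Move to photopic testing.** "After scotopic testing, the light of the OCD will be increased and light-adapted (photopic) testing will be performed in the same manner". Neither an interval nor a luminance is given.

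No step asks staff to record how long each eye was dark- or light-adapted. Section G2 lists scotopic contrast, photopic contrast and their within-eye comparison among the primary expected comparisons, between eyes and then among groups.

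**The concern.** The measured quantities are thresholds that depend on how far the eye has adapted. If adaptation is still under way when testing starts, a participant tested at 20 minutes and one tested at 30 are not measured under the same condition, and neither are the first and second eyes of one participant.

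Two consequences need to be kept apart. Variation in waiting time between participants is noise, unless it differs systematically by group. The lag between eyes is systematic: where one eye always goes first, any remaining drift appears as a left-right difference, and more participants will not remove it. The photopic test adds a further gap. During the first eye's photopic test the second eye is either covered or exposed to the light, so its state depends on a choice that F2 leaves open.

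What is at stake is the primary comparisons themselves, and also the use of Study 1 in Section G2 to judge whether the Study 2 sample size is appropriate.

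**Working it through.** **Inputs from the documents.** Dark time D = 20-30 min (F2). Test time t = 3-5 min per eye (Section C). Group size is 20 (G1). The plan states no alpha, power, effect size, SD or drift rate, so it has no figure to reproduce.

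**Assumption on timing.** The protocol does not say whether t applies to each lighting condition. I take it that it does, and ignore changeover time. If t covers both conditions together, the lags below are shorter.

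**Timing.**
- First scotopic eye starts at D = 20-30 min.
- Second scotopic eye starts at D + t = 23-35 min.
- Photopic testing starts no earlier than D + 2t = 26-40 min, plus an unstated light-adaptation interval.
- During the first photopic test the second eye receives no device light if covered, or 3-5 min of it if uncovered.

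In Study 1 the second eye is always the right eye, so eye and lag cannot be separated. In Study 2, reversing the order means each eye is first once, but for a given eye order then changes with visit. G2 does not plan to average the visits.

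**Illustration (assumptions, not document figures).** Two-sided alpha is 0.05, D is uniform on 20-30 min, and the threshold drifts linearly by b SD per minute, where SD is the between-person SD at a fixed adaptation time.

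- Variance of D = 10²/12 = 8.33 min² (SD 2.89 min). Added variance fraction v = 8.33 b².
- With 20 per group, the standardised difference detectable with 80% power is √(2/20) × (1.960 + 0.842) = 0.886 (normal approximation; 78% power by t test). Power with added noise = Φ(0.886/√(0.1(1 + v)) − 1.960).
- Between-eye shift = b × (3 to 5).
- Chance that a paired test in 20 people declares a left-right difference when there is none: SD of the difference = √(2(1 − ρ)), with between-eye correlation ρ of 0.5 or 0.8 (assumed).

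| b (SD/min) | v | Power | Between-eye shift (SD) | False positive, ρ = 0.5 | False positive, ρ = 0.8 |
|---|---|---|---|---|---|
| 0 | 0 | 80.0% | 0 | 5% | 5% |
| 0.01 | 0.1% | 80.0% | 0.03-0.05 | 5.2-5.6% | 5.5-6.4% |
| 0.02 | 0.3% | 79.9% | 0.06-0.10 | 5.8-7.3% | 7.1-10.9% |
| 0.05 | 2.1% | 79.2% | 0.15-0.25 | 10.3-20.1% | 18.6-42.4% |
| 0.10 | 8.3% | 76.8% | 0.30-0.50 | 26.9-60.9% | 56.4-94.2% |

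Under linear drift the starting time cancels from one person's between-eye difference, since b(D + t) − bD = bt. The window therefore matters for comparisons among people, and the lag for comparisons between eyes.

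**Group comparison, only if mean adaptation time differs.** A 5-minute difference in means (assumed) shifts the contrast by 5b = 0.05, 0.10, 0.25 or 0.50 SD for the four non-zero drifts. The false-positive rate is then about 5%, 6%, 12% or 33%. With no difference in means it stays at 5%.

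These figures concern dark adaptation only. Nothing in the documents allows the photopic or covering effect to be sized.

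**The case against.** The case on the other side is substantial.

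1. *Light adaptation is intended.* The protocol calls the photopic test light-adapted. A reader might infer that the first eye is tested with no time to adapt, or that photopic values come from dark-adapted eyes. The documents do not support that: they leave the interval unstated, and silence is not zero. This objection stands, and the point is limited accordingly.
2. *Testing is monocular and the device has a blocking screen.* Covering may therefore be uniform in practice. This makes covering the weakest part, but F2 still words it as optional.
3. *Group bias is not shown.* All groups share the same window, and nothing says that staff volunteers and patients wait for different times. This stands. One possible route is in the text: at Study 2 Visit 1, perimetry comes before dark adaptation, and only glaucoma patients with a good field from the previous 6 months may skip it. That shows how light exposure beforehand could differ by group, not that adaptation does differ when testing starts.
4. *The noise may be trivial.* This stands for shallow drift. A reader might instead infer a large variance inflation, such as 75%. That needs 8.33 × 0.30² = 0.75, a drift of 0.30 SD per minute, for which the documents give no basis.
5. *Study 1 exists to refine the procedure.* Five volunteers are tested first, and debriefing covers dark adaptation. That is a fair reason for some latitude early in Study 1. But Study 2 repeats the open wording, and no step commits the team to closing it.
6. *Eye order is reversed at the second Study 2 visit.* This is a partial safeguard. Study 1 has none.

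**Conclusion.** The point holds in this form. In both studies the adaptation state at testing is not fixed and its timing need not be recorded, so it can differ between participants and between eyes. The result is avoidable noise in the scotopic, photopic and ratio comparisons. The Study 1 between-eye comparison is biased if thresholds are still drifting, because eye is fully confounded with a lag of about 3-5 minutes and with possible light exposure. Group comparisons are biased only if adaptation differs by group, which the documents do not show.

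The size is unknown. At assumed drifts up to 0.10 SD per minute, noise from the window lowers power from 80% to no less than 76.8%, which is minor. The between-eye shift, at 0.03-0.5 SD, ranges from negligible to serious. If drift between 20 and 35 minutes is zero, neither dark-adaptation effect arises, though the open photopic step remains. The change is worth making before enrolment, because adaptation times that were never recorded cannot be adjusted for later.

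**What to change.** In Section F2, for both studies:

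- Set one dark-adaptation time within the stated range and apply it to everyone.
- Apply the same fixed, timed light-adaptation interval at the photopic level immediately before *each* eye's photopic test. A single interval before the first eye would not do, because a covered second eye could lose its light adaptation while it waits.
- Use one covering rule for the non-tested eye, for example the device's own blocking screen.
- Alternate which eye is tested first across Study 1 participants. Fixing the dark time does not remove the second-eye lag; alternation stops it from being tied to one eye.
- Record actual dark and light times and eye order, and name them in G2 as covariates.

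**Cost.** A few extra minutes per visit. Four tests of 3-5 min take 12-20 min. With 30 min of dark adaptation that is 42-50 min, leaving 10-18 of Study 1's approximately 60 min for consent, history, acuity, demonstration, light intervals and debriefing, which is tight. With 20 min, 20-28 min remain. The 90-minute first research visit in Study 2 leaves 40-48 min even with the longest time. Alternating order and recording times cost almost nothing.
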